4. PARTICIPANT ENTRY

4.1 PRE-REGISTRATION EVALUATIONS

Potential participants will have their notes screened by NHS team members to identify patients that meet the inclusion / exclusion criteria. They will then be asked if they are happy to talk to the research team to discuss the project and undergo informed consent to take part.

4.2 INCLUSION CRITERIA

Referred to the Imperial Weight Centre (NHS) Tier 4 service team for consideration bariatric surgery (RYGB / VSG / mRYGB / LAGB), Obese (BMI>30kg/m²), Age ≥18, failure of efforts at lifestyle modification and dieting, fitness for anaesthesia and procedure, willingness to comply with the trial protocol.

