The gut microbiome has now been linked extensively with numerous disease states and it represents a novel therapeutic target in the treatment of obesity³. A low bacterial richness in the gut is associated with increased adiposity, insulin resistance and dyslipidaemia⁴. Indeed metagenome wide association studies have demonstrated the ability to identify T2DM patients based on their gut microbiome⁵. Convincingly, in an effort to establish causality, the colonisation of germ free mice with the faecal microbiota of twin pairs discordant for obesity results in significantly greater increases in body mass and adiposity in mice receiving the faecal microbiota from the obese twin⁶. However, the overwhelming disruption to the gut microbiome caused by bariatric surgery is only just being defined, as is its functional importance. This has been demonstrated in faecal transplant experiments using the gut microbiota from Roux-en-Y gastric bypass (RYGB) treated mice to transplant non-operated germ free mice, leading to significant weight loss and decreased fat mass compared to transfer of the gut microbiota from mice who had undergone sham surgery⁷. This is thought to be through mechanisms including: reduced energy harvest of non-digestible food types such as complex carbohydrates and plant polysaccharides, increased gut permeability leading to increased systemic inflammation, altered bile acid metabolism and carbohydrate fermentation products such as short-chain fatty acids acting as signalling molecules to increase satiety^{8,9}. In particular BAs have emerged as key signalling molecules, acting through the Farnesoid X Factor nuclear receptor (FXR) and G protein-coupled bile acid receptor (TGR5) to induce a number of physiological changes including; increased incretin release, improved glucose homeostasis, improved satiety, altered gut microbiota – acting in a bi-directional way, and increased metabolic rate^{10,11}. In support of this, many of the beneficial effects seen after RYGB are reproduced in rats by simply diverting bile from the common bile duct to the mid to distal jejunum via a catheter¹⁰. Additionally, following Vertical Sleeve Gastrectomy (VSG) in mice, body fat is reduced and glucose tolerance improved compared to sham-operated controls. However, body fat and glucose tolerance do not significantly differ in FXR knockout mice after VSG. Furthermore, *Bacteroides* were reduced following VSG in the wild type mice but the gut microbiota was not altered in the FXR knockout mice suggesting that FXR signalling is important in mediating the beneficial effects of VSG, in part through its modulation of the gut microbiota¹¹.

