
1.2 RATIONALE FOR CURRENT STUDY

From a clinical perspective, national and international guidelines for bariatric surgery have historically been based predominantly on weight. However, bariatric surgery is also highly successful in achieving remission of co-morbidities such as T2DM. The chance of remission does not appear to be weight dependent. In a recent meta-analysis T2DM remission was 72% in patients with a BMI < 35 kg/m² and 71% in patients with a BMI > 35 kg/m² undergoing bariatric surgery¹². Consequently, the latest guidelines by NICE in the UK have been updated to reflect the convincing body of evidence that surgery is also a highly successful and cost-effective treatment for T2DM patients who are less obese. As many as 2 million patients may be eligible for bariatric surgery under these new guidelines. However, unfortunately up to 30% of T2DM patients who undergo bariatric surgery do not achieve remission of their T2DM. There is currently no reliable method of identifying these patients preoperatively. T2DM remission does not appear to correlate with preoperative BMI or any other known clinical or biochemical marker reliably. Therefore novel preoperative biomarkers to help guide clinicians and policy makers select the ideal surgical candidates are urgently required to enable truly personalised healthcare.

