2. STUDY OBJECTIVES

We hypothesise that weight loss and the metabolic effects of bariatric surgery are achieved in part through a functional modification of the gut microbiome and altered microbiome – host metabolome interactions. We aim to elucidate these and other mechanisms of T2DM remission following bariatric surgery. We will explore both the weight dependent and weight independent mechanisms with the translational objectives of 1) identifying novel, surgical and non-surgical, therapeutic targets and 2) identifying novel biomarkers for preoperative prognostication of T2DM remission.

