7. STATISTICS AND DATA ANALYSIS

Multivariate statistical analysis will be performed on the generated metabonomic and metagenomic data sets. This will include unsupervised principal components analysis (PCA) and supervised partial least squares discriminant analysis with orthogonal signal correction (OPLS-DA) and O2-PLS between data sets. Mapping T2DM outcomes to metabonomic and metagenomic data will potentially identify novel preoperative biomarkers that are able to prognosticate T2DM resolution following bariatric surgery.

Due to the complexity of metabonomic data sample size calculations are difficult and there is currently no standardised technique. We used peer-reviewed MetSizeR methodology to calculate appropriate sample sizes¹³. Using principal component analysis on an expected metabonomic data set of 300 metabolites of which 20% differentiate significantly and a targeted false discovery rate of 5%, over 15 samples are needed in each group.

Approximately 30% of obese diabetic patients do not have resolution of disease following bariatric surgery¹². To allow for an expected drop out rate of 20% at 1 year we will recruit 65 patients undergoing RYGB and 65 patients undergoing VSG to achieve 15 patients with non-resolution of diabetes and 36 patients with resolution in each surgical group. We will also aim to recruit 65 non-diabetic patients undergoing surgery to act as a control group. This will enable comparison against diabetic patients that undergo remission after surgery.

Four surgeons at the Imperial Weight Centre collectively perform approximately 220 RYGB and 180 VSG procedures a year. In previous years 25% of patients have had T2DM. However, we expect this percentage to rise since the introduction of new NICE guidelines encouraging bariatric surgery in diabetic patients in November 2014. We expect to recruit 1-2 patients a week that meet the inclusion criteria and have completed recruitment after 18 months.

Data and all appropriate documentation will be stored for a minimum of 10 years after the completion of the study, including the follow-up period.

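### The comparison of non-diabetic controls with diabetic remitters has no matching or adjustment for BMI, although the protocol's own account of referral suggests the controls may be heavier

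*Combined protocol and SAP*

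**What the plan says.** Section 4.2 sets a single entry rule for every participant, "Obese (BMI>30kg/m²), Age ≥18, failure of efforts at lifestyle modification and dieting", together with referral to the surgical service. It does not distinguish diabetic from non-diabetic patients.

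Section 1.2 explains that guidelines were historically driven mainly by weight and were then updated to recognise that "surgery is also a highly successful and cost-effective treatment for T2DM patients who are less obese". Section 7 adds, about the diabetic share of the caseload, that "we expect this percentage to rise since the introduction of new NICE guidelines encouraging bariatric surgery in diabetic patients".

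On the control group, section 7 states: "We will also aim to recruit 65 non-diabetic patients undergoing surgery to act as a control group". Its purpose follows: "This will enable comparison against diabetic patients that undergo remission after surgery". The methods listed are PCA, OPLS-DA and O2-PLS. No matching variable, stratification factor or covariate is named for this or any other contrast.

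Two further statements bear on the point. Section 1.1 says: "A low bacterial richness in the gut is associated with increased adiposity, insulin resistance and dyslipidaemia". Section 2 says: "We will explore both the weight dependent and weight independent mechanisms".

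**The concern.** If a newer route to surgery exists for less obese patients, and that route depends on having type 2 diabetes, the lower part of the BMI range may contain more diabetic than non-diabetic patients. The controls would then tend to start heavier than the diabetic remitters they are compared with.

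The protocol itself says that adiposity goes with one of the things being measured. OPLS-DA is supervised: it looks for whatever separates the two classes, and a difference in starting BMI is one candidate. A control of the false discovery rate guards against chance findings, not against a systematic imbalance between groups.

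The error could go either way. A feature related to BMI but not to diabetes could appear to mark diabetes status. Conversely, section 1.1 associates low richness with both adiposity and insulin resistance, so heavier controls could resemble diabetic patients and hide a real difference. In either case an unadjusted result could not separate weight-dependent from weight-independent differences, which section 2 sets out to explore. The control cohort is one third of planned recruitment (65 of 130 + 65 = 195).

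**Working it through.** **The plan's own figures.** Section 7 recruits 65 diabetic patients per operation, expects 20% dropout at 1 year and takes 30% as not resolving.

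- Completers: 65 × (1 − 0.20) = 52
- Not resolved: 52 × 0.30 = 15.6 (plan: 15)
- Resolved: 52 × 0.70 = 36.4 (plan: 36)

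These reproduce. The plan gives no calculation for the control contrast and no BMI distribution for either cohort, so what follows is an illustration.

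**Inputs**

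- Remitters: 2 × 36 = 72 (section 7).
- Controls: 65 × 0.80 = 52. Applying the 20% dropout to controls is an assumption.
- BMI gap between cohorts, d: 0.3 to 0.5 SD (assumption).
- Correlation of a feature with BMI, r: 0.1 to 0.5 (assumption).
- The feature has no relation to diabetes, and the test is two-sided at a nominal 5%.

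**Formulas**

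- Spurious difference in SD units = r × d
- SE = √(1/72 + 1/52) = 0.182 SD
- Shift s = r × d / SE
- Rejection probability = P(Z > 1.96 − s) + P(Z < −1.96 − s)

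**Results**

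| d (SD) | r | r × d | s | Rejection |
|---|---|---|---|---|
| 0.3 | 0.1 | 0.03 | 0.16 | 5.3% |
| 0.3 | 0.3 | 0.09 | 0.49 | 7.8% |
| 0.3 | 0.5 | 0.15 | 0.82 | 13.1% |
| 0.5 | 0.1 | 0.05 | 0.27 | 5.9% |
| 0.5 | 0.3 | 0.15 | 0.82 | 13.1% |
| 0.5 | 0.5 | 0.25 | 1.37 | 27.9% |

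At the weak end the effect is negligible. At the strong end a feature unrelated to diabetes is flagged more than five times as often as the nominal 5%.

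**A second illustration.** Here 10% to 30% of diabetic patients are assumed to lie in a low-BMI stratum that contains no controls, 8 to 12 kg/m² below the rest, with a BMI SD of 6.5.

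- BMI gap: from 0.10 × 8 = 0.8 to 0.30 × 12 = 3.6 kg/m², that is 0.12 to 0.55 SD.
- With r from 0.1 to 0.3, and 73 remitters (2 × 36.4) against 52 controls, rejection is 5.1% to 15.0%.
- Section 7 assumes 300 metabolites of which 20% differentiate, leaving 240 that do not. If all 240 had such a correlation, about 12 to 36 would be flagged, against 240 × 0.05 = 12 with no BMI gap.

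**Limits of the check.** A nominal test of one feature is a simple proxy for OPLS-DA and is not the planned analysis. It covers false positives only; masking of a true difference is not quantified.

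**The case against.** The strongest reply is that the premise is inferred. No section gives a BMI threshold for non-diabetic referral or a BMI distribution by cohort. Section 7 expects more diabetic patients but does not say there that they will be lighter. The association in section 1.1 is not stated to hold within a cohort that is entirely obese. This stands: heavier controls are plausible but not shown, and the bias may be negligible.

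A second reply is that section 1.2 reports nearly equal remission below and above a BMI of 35 (72% and 71%). Those are remission rates in operated diabetic patients. They do not show that the microbiome or metabolome is unrelated to BMI.

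Third, section 7 does not say whether the contrast uses preoperative samples, postoperative samples or change. With preoperative samples all 65 controls might contribute. The SE would then be √(1/72 + 1/65) = 0.171 and the range about 5% to 31%, so the conclusion is the same. With change, stable baseline differences would partly cancel. This uncertainty stands.

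Fourth, removing BMI from every feature could remove real signal, because weight-dependent mechanisms are also of interest. This is a fair reason not to replace the unadjusted analysis, and the adjusted one should stand beside it.

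A reader might also infer more than the documents support:

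- *That the BMI floor in section 4.2 is at fault.* It is not. A common floor helps comparability; the gap is in section 7.
- *That age and sex are confounded too.* The referral argument concerns BMI only, and nothing in the documents suggests that age or sex differs between cohorts.
- *That inflation of at least 13% is established.* That needs a correlation near 0.5, or a wide gap with a correlation of about 0.3. Weaker values bring it close to 5%.
- *That the main result is compromised.* The primary outcome and the sample size rest on remission versus non-remission within diabetic patients, where the controls play no part.

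**Conclusion.** The point holds as a gap in section 7. The control-versus-remitter contrast has no matching or adjustment for BMI, while the protocol describes a route to surgery that could make the cohorts differ in BMI and says that adiposity is associated with gut richness. BMI may therefore confound this contrast, and an unadjusted result cannot support a claim of a weight-independent difference.

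The direction (heavier controls) is inferred and the size is unknown. Under the stated assumptions, the chance of falsely flagging a feature unrelated to diabetes lies between about 5% and 28%, so the effect ranges from negligible to material. No figure in the plan is wrong. The change is worth making because the data needed to settle the question will already be in hand.

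**What to change.** In section 7:

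1. Report baseline BMI by cohort.
2. Say which samples the control-versus-remitter contrast uses (preoperative, postoperative or change).
3. Present that contrast both unadjusted and adjusted for preoperative BMI. One way is to estimate each feature's BMI slope in a model that also contains cohort, subtract the BMI part, and then run the multivariate model. Age and sex may be added as standard covariates, but this point does not depend on them.
4. Repeat the contrast in the BMI range where both cohorts overlap.
5. Claim a weight-independent difference only if it persists after adjustment.

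The eligibility floor in section 4.2 stays unchanged. Frequency-matching controls to diabetic patients on BMI is optional, and only possible if recruitment is still open, which the documents do not show.

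The cost is small. Weight and BMI are already outcome measures in the study summary, and section 6 already retrieves clinical data from the notes from before surgery. The change needs new wording, a little more analysis and a few degrees of freedom. The overlap analysis loses some precision because it uses fewer patients.

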4.3 EXCLUSION CRITERIA

Previous bariatric surgery, previous major abdominal surgery*, pregnancy or intention to become pregnant during trial period, lack of capacity to consent.

* = Small or large bowel resection, liver, pancreatic or splenic surgery, as these will influence the bacteria in the gut and / or the patient's metabolic state, which we are studying. It will not include patients that have previously had an appendicectomy, cholecystectomy, hernia repairs or surgery on other organs not listed above.

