3.1 STUDY OUTCOME MEASURES

The 1^o clinical outcome measure will be diabetes remission defined as HbA1c < 42 mmol/mol. The 2^o clinical outcomes will be partial diabetes remission (HbA1c < 48 mmol/mol), HbA1c reduction and % excess weight loss.

These clinical outcomes will be mapped to metabolomic and metagenomic data to identify preoperative markers of diabetes remission and weight loss.

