6. ASSESSMENT AND FOLLOW-UP

Patients will undergo follow up according to the usual bariatric surgery follow up protocol at the Imperial Weight Centre.

- At patients usual preoperative, 3 month, 1 and 2 year postoperative outpatient appointments patients will provide additional samples of blood, urine and faeces for analysis.
- Patients will be given brief online 24-hour diet recall questionnaires to complete while waiting for their usual outpatient appointments. They will then be asked to complete entries for two days following each hospital visit using a personal computer via a personal link to a secure website provided.
- Patients will be sent home with 24-hour urine collection bottles. They will be asked to provide 24-hour collections for before surgery and the days before their 3-month and 1-year outpatient visits. They will be able to return their samples when they attend these appointments.
- At the time of surgery researchers will collect resected stomach tissue from LSG patients that would usually be disposed.
- Clinical data will be retrieved from the medical notes preoperatively to 2 years postoperatively.

Study End: 130 type 2 diabetic and 65 non-diabetic patients will be recruited and followed-up until 2 years postoperatively.

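### The omics contrasts carry no drug-exposure term, so effects of glucose-lowering treatment could be reported as diabetes, mechanistic or new remission markers, above all in the control comparison

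*Combined protocol and SAP*

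**What the plan says.** Section 4.3 lists its exclusions as "Previous bariatric surgery, previous major abdominal surgery*, pregnancy or intention to become pregnant during trial period, lack of capacity to consent". A footnote limits the abdominal item to bowel resection and liver, pancreatic or splenic surgery, "as these will influence the bacteria in the gut" or the metabolic state under study, and keeps patients with lesser operations such as appendicectomy or hernia repair. Neither 4.2 nor 4.3 mentions medication.

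Section 6 schedules blood, urine, faeces and diet recall around the outpatient visits. It adds that "Clinical data will be retrieved from the medical notes preoperatively to 2 years postoperatively". No drug item, antibiotic look-back or timing of samples relative to drugs is named.

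Section 7 describes the analysis as follows: "This will include unsupervised principal components analysis (PCA) and supervised partial least squares discriminant analysis with orthogonal signal correction (OPLS-DA) and O2-PLS between" data sets. Its stated purpose is that "Mapping T2DM outcomes to metabonomic and metagenomic data will potentially identify novel preoperative biomarkers". No covariate, stratification or sensitivity analysis is given. The 65 non-diabetic controls are to be compared with diabetic patients who remit. Section 3.1 gives the primary outcome as "diabetes remission defined as HbA1c < 42 mmol/mol", with no condition on treatment.

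**The concern.** Drugs present at sampling can alter the faecal, urine and blood profiles that the study measures. Glucose-lowering treatment follows diabetes status, so the control contrast, if made on preoperative samples, is close to treated against untreated. Between remitters and non-remitters, treatment may differ through disease severity. Because remission is defined on HbA1c alone, postoperative treatment may also differ within and between the outcome groups.

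OPLS-DA is supervised: it finds whatever separates the classes, treatment included. Followed as written, the analysis could present a feature of the drug regimen as a feature of diabetes, a mechanism or therapeutic target (section 2), or a new preoperative marker (section 1.2). In the last case the open question would be whether the marker tells the clinician anything beyond the prescription record.

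**Working it through.** **Group sizes in section 7.** Inputs: 65 recruited per operation, 20% dropout, 30% non-resolution.
- Evaluable: 65 × 0.80 = 52.
- Non-resolvers: 52 × 0.30 = 15.6. Resolvers: 52 × 0.70 = 36.4. The stated 15 and 36 reproduce.
- Pooled over both operations: 30 v 72. Controls, if the same 20% dropout is assumed: 65 × 0.80 = 52.

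The MetSizeR requirement of over 15 per group cannot be re-derived, because its simulation settings are not given.

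**Spurious shift.** Shift = (difference in proportion exposed) × (drug effect in SD). The documents give neither input; both are assumptions.
- Non-remitters v remitters: gaps of 20 to 50 points × 0.5 to 1.0 SD = 0.10 to 0.50 SD.
- Remitters v controls: use of 50-90% v 2%, so gaps of 48 to 88 points × 0.5 to 1.0 SD = 0.24 to 0.88 SD.

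**What that does to false findings.** Simulation, 300 data sets per scenario: 300 independent unit-variance metabolites, none truly linked to outcome, and 60 of them (20%, borrowing the plan's fraction) shifted by the drug. Groups were compared by t-test, then by regression with a drug term, with Benjamini-Hochberg control at the plan's 5%. This is a univariate stand-in for OPLS-DA. Ranges run over drug effects of 0.5 and 1.0 SD.

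| Contrast | Assumed use | Drug-affected metabolites at p<0.05, no drug term | Data sets with at least one false discovery |
|---|---|---|---|
| 15 v 36 | 50% v 50% | 5% | 3-6% |
| 15 v 36 | 60% v 40% | 6-9% | 7-8% |
| 15 v 36 | 70% v 40% | 8-14% | 11-14% |
| 15 v 36 | 80% v 30% | 13-32% | 12-41% |
| 30 v 72 | 80% v 30% | 19-56% | 22-81% |
| 72 remitters v 52 controls | 50-90% v 2% | 25-100% | 34-100% |

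In the control contrast the mean number of false discoveries runs from 0.6 to 61. With a drug term, the p<0.05 rate among affected metabolites is 4.7-5.3% in every scenario.

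Hand check of one cell (15 v 36, 80% v 30%, 1 SD). The group variances are 1 + 0.8 × 0.2 = 1.16 and 1 + 0.3 × 0.7 = 1.21. The pooled SD is about 1.09, and the standard error is 1.09 × √(1/15 + 1/36) ≈ 0.34. Then 0.50/0.336 ≈ 1.49, and the chance of exceeding 1.96 is about 32%, as simulated.

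**What the checks can support.** If 80% of remitters take a drug class (assumption), untreated remitters number 0.2 × 36 ≈ 7 per operation, or 0.2 × 72 ≈ 14 pooled. At 50% use the figures are 18 and 36.

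**Excluding exposed patients instead.** Assumed losses of 10, 20 and 30% leave 15.6 × 0.9 = 14.0, 15.6 × 0.8 = 12.5 and 15.6 × 0.7 = 10.9 non-resolvers per operation, below the plan's target. Restoring 15.6 would need 65/0.9, 65/0.8 and 65/0.7, that is 73, 82 and 93 recruits per operation.

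**The case against.** Several stronger readings are tempting, and the documents do not support them.

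- A reader might infer that the plan breaks its own principle by excluding surgery and ignoring drugs. Section 4.3 is a bounded list of operations that expressly keeps others. It shows that the investigators recognise such exposures, but it states no general rule. The plan is silent on drugs, which is different from contradicting itself.
- A reader might infer that drug data will not be collected. The notes retrieved under section 6 may well hold prescriptions, and section 7 is an outline whose list of methods is not closed. What can be said is that drug use is not pre-specified in any contrast.
- A reader might infer that a drug-linked marker is worthless. For prognosis this does not follow, since such a marker can still predict remission. The question there is added value. Confounding bears more on the mechanistic aim and the control contrast.
- A reader might infer that antibiotics bias the contrasts. Nothing in the documents suggests that their use differs between groups, and with equal use the simulation shows no inflation.

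Against the size: no figure for drug use or drug effect comes from the trial. At 15 v 36 with modest imbalance the inflation is small, and marked inflation needs something like 80% v 30%. Section 1.2 says that no known clinical marker reliably tracks remission, which argues against assuming a large treatment gap between outcome groups. Section 7 does not say at which visit the control contrast is made; postoperatively, treatment among remitters may be lower than assumed here.

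Against the remedy: if treatment follows severity, adjusting for it can remove real signal, and 15 non-resolvers will not carry several drug-class terms.

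All of this stands. It limits the claim and shapes the remedy, but it leaves the unadjusted contrasts unable to separate treatment from disease.

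**Conclusion.** The point holds in limited form and should be acted on. It is strongest for non-diabetic controls against remitted diabetic patients, because treatment there follows the grouping itself. It is plausible but smaller for remitters against non-remitters, where it depends on an imbalance that the documents do not establish. For antibiotics the expected effect is noise.

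The shifts and false-discovery rates are illustrations. They rest on assumed drug use, an assumed effect of 0.5 to 1 SD, independent metabolites and a univariate analysis. They show that the problem can range from negligible to dominant, and that the plan as written has no means of telling which applies. The recovery to about 5% with a drug term also belongs to that simple model. In the control contrast, adjustment would rest on few overlapping patients.

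**What to change.** At each sampling visit, extract glucose-lowering drug use and recent antibiotic use from the notes already being retrieved. State the antibiotic look-back in advance and give its basis; the documents supply none. Keep the planned unadjusted analysis. For the features it selects:

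1. Report remitter v non-remitter results with and without one simple treatment covariate, and test whether the marker adds to preoperative treatment in predicting remission. This can be done by regression on the selected features, leaving OPLS-DA and O2-PLS unchanged.
2. Check whether control-contrast findings persist among diabetic patients not on the drug class, pooled across operations and labelled exploratory because numbers are small.
3. Repeat the analysis without samples that fall in the antibiotic window.

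State at which visit each contrast is made.

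The cost is a few extraction fields and secondary analyses, with no new patients, visits or exclusion criteria. The downsides should be written into the plan: lost precision with about 15 non-resolvers per surgical group, and possible removal of severity-related signal, which is why adjusted and unadjusted results belong side by side.
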